3.2 Exclusion Criteria

At time of registration, patient must lack the following exclusion criteria:

- 1) Inability to provide informed consent
- 2) Hypersensitivity to temozolomide or HD IL-2
- 3) Active gastrointestinal disorders or cardiac disorders i.e. cardiac failure, MI within 6 months as determined by the investigator
- 4) EF < 50% by echo or corrected DLCO < 50% on diffusion capacity testing PFTs
- 5) PLT < 100K, ANC < 1000
- 6) Chronic use of steroids other than for simple adrenal replacement

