3.1 Inclusion Criteria

At time of registration, patients must have following inclusion criteria:

- 1) Metastatic malignant melanoma, pathologically confirmed
- 2) Age \geq 18 years and ability to provide informed consent
- 3) ECOG Performance Status of 0 or 1
- 4) Patients should be considered good candidates, i.e. ECOG <2 , Creat <2 Bilirubin <2 for conventional high dose IL-2
- 5) No chemotherapy, hormonal therapy, immunotherapy or radiation therapy within 1 month of entry
- 6) Patients with a history or clinical evidence of brain metastasis must have completed radiation therapy or surgical treatment of brain lesions and have no evidence of CNS progression for at least eight weeks at the time of enrollment. Patients must not require corticosteroids for treatment of cerebral edema for brain metastases. Patients must be evaluated with a head MRI within 4 weeks prior to enrollment.
- 7) Patients may have had prior high dose IL-2 or temozolomide but not together or with high dose IL-2 followed by temozolomide
- 8) Patients may have had prior high dose interferon as adjuvant treatment for high risk Melanoma
- 9) Serum Cr < 2 mg/dL
- 10) Bilirubin < 2 mg/dL (except for Gilbert's Syndrome)

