4.2.2 Temozolomide Drug Information

Temozolomide is a synthetic atypical alkylator. It can cross the blood brain barrier and has excellent bioavailability. Patients would be given Zofran and Compazine as antiemetic support.

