5.0 TRIAL PROCEDURES

5.1 Screening and Consent

Patients with metastatic melanoma seen in the PSHCI clinic who are considered good candidates for high dose IL-2 therapy will be asked to participate in this trial and their eligibility will be reviewed using the inclusion and exclusion criteria noted. After explanation of the nature and logistical aspects of the study, patients will be asked to review the consent document carefully. If they have any questions regarding any aspect of the study, these will be answered to the satisfaction of the patient. The patient will sign the consent document to verify that they are fully interested in participation in the study as defined by the consent form. An eligibility checklist will be completed and signed by study personnel after consent has been executed (Appendix I Eligibility Checklist). The demographics and clinical plan data will be recorded on forms (Baseline Interval Form) (Recist 1.1 Measurement Form)

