NOTE: The term disability means a substantial disruption of a person's ability to conduct normal life functions. This definition is not intended to include experiences of relatively minor medical significance such as uncomplicated headache, nausea, vomiting, diarrhea, influenza, and accidental trauma (e.g. sprained ankle) which may interfere or prevent everyday life functions but do not constitute a substantial disruption.

e. Is a congenital anomaly/birth defect

f. Medical or scientific judgement should be exercised in deciding whether reporting is appropriate in other situations, such as important medical events that may not be immediately life-threatening or result in death or hospitalization but may jeopardize the subject or may require medical or surgical intervention to prevent one of the other outcomes listed in the above definition. These should also be considered serious. Examples of such events are invasive or malignant cancers, intensive treatment in an emergency room or at home for allergic bronchospasm, blood dyscrasias or convulsions that do not result in hospitalization, or development of drug dependency or drug abuse.

Clinical Laboratory Abnormalities and Other Abnormal Assessments as AEs and SAEs

Abnormal assessments (e.g., ECGs, X-rays, and vital signs) that are judged by the investigator as clinically significant will be recorded as AEs or SAEs if they meet the definition of an AE or SAE. Abnormal laboratory findings < Grade 3 (per CTCAE version 4) will only be recorded if

deemed clinically significant by the investigator. Clinically significant abnormal laboratory findings or other abnormal assessments present at baseline which significantly worsen following the start of the study will be reported as AEs or SAEs. However, clinically significant abnormal laboratory findings or other abnormal assessments that are associated with the disease being studied, unless judged by the investigator as more severe than expected for the subject's condition, or that are present or detected at the start of the study and do not worsen, will not be reported as AEs or SAEs.

The investigator will exercise his or her medical and scientific judgment in deciding whether an abnormal laboratory finding or other abnormal assessment is clinically significant.

Time Period, and Frequency of Detecting AEs and SAEs

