² – Patients with or without known brain metastases can get an MRI at any time, should they develop neurological Symptoms as determined by the investigator

³ – Will include ESR, CRP, ANA, RF and TSH

⁴ – Will include flow cytometry, Elispot, flow- based tetramer analysis (To be processed by [name]'s lab [name])

⁵ CBC, diff, platelets, CMP, LDH,

⁶ – This scheme will be repeated up to 4 courses

⁷ – CRP only

⁸ - Post-cycle labs will be drawn 24-72 hours after completion of the last dose of IL-2 for each cycle. These may be obtained while the patient is admitted, as long as it falls within the 24-72 hour timeframe and has been arranged with the study coordinator.

One Course is comprised of 2 cycles of high dose IL-2 followed by 4 weeks off, then 3 weeks of continuous low dose oral temozolomide, with another 2 weeks off prior to reimaging (approximately 12 weeks in duration from start to finish)

Study Schema Algorithm: Phase II Trial of High Dose Interleukin-2 followed by intermittent low dose Temozolomide in patients with Metastatic Malignant Melanoma

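### The eligibility criteria, signed checklist and schedule of events are silent on pregnancy and breast-feeding, and no pregnancy test is scheduled before high dose IL-2 or temozolomide.

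*Combined protocol and SAP*

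**What the plan says.** Entry is governed by two lists. Section 3.1 has ten inclusion items; the only demographic one sets a minimum age of 18 together with "ability to provide informed consent". Section 3.2 begins "At time of registration, patient must lack the following exclusion criteria" and gives six items, ending with "Chronic use of steroids other than for simple adrenal replacement". Section 5.1 adds a control on their use: "An eligibility checklist will be completed and signed by study personnel after consent has been executed". The checklist in the appendices has ten inclusion and six exclusion lines that largely repeat 3.1 and 3.2.

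Baseline testing in 5.2 covers blood count, metabolic panel, LDH, an autoimmune panel, correlative samples, imaging, brain MRI, echocardiogram and lung function. In Appendix III, footnote 5 defines routine labs as "CBC, diff, platelets, CMP, LDH", and footnote 3 limits the autoimmune panel to ESR, CRP, ANA, RF and TSH.

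On the drugs, 4.2.2 states "Temozolomide is a synthetic atypical alkylator". Section 5.3 allows up to four courses, each with two IL-2 cycles and 21 days of temozolomide. Section 7.0 includes "Is a congenital anomaly/birth defect" among its criteria for a serious adverse event.

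**The concern.** Eligibility lists decide who may be treated, and the schedule decides what is looked for first. Here both are silent on a patient type that could plausibly present, since entry is open to any adult with metastatic melanoma who meets the organ-function limits. If such a patient were enrolled, she would receive a cytokine whose described effects include high fever, hypotension and capillary leak (4.1.2), followed by an alkylator. What is at stake is the safety of that patient, a fetus or a nursing infant. The statistical inference is not at stake.

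**Working it through.** No figure in the plan bears on this point, so the check is a reading of each place where a provision could stand, followed by simple arithmetic on exposure and timing.

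**Where a provision could stand**

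| Place | Content | Pregnancy, breast-feeding or pregnancy test? |
|---|---|---|
| 3.1 | 10 inclusion items | None |
| 3.2 | 6 exclusions: consent, hypersensitivity, GI/cardiac, EF/DLCO, platelets/ANC, steroids | None |
| Eligibility checklist | 10 inclusion and 6 exclusion lines | None |
| 5.2 | Baseline labs, imaging, cardiopulmonary tests | None |
| Appendix III and footnotes | Routine labs, autoimmune panel, immunoassays, imaging | None |
| 4.1 and 4.2 drug sections | Dosing, drug information, toxicities | No mention of reproductive toxicity |
| 7.0 | Criteria for a serious event | Birth defect, as one of the criteria a to f |

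**Could another clause fill the gap?** The nearest candidate is inclusion item 4: "Patients should be considered good candidates, i.e. ECOG <2 , Creat <2 Bilirubin <2 for conventional high dose IL-2". The words after the abbreviation restrict its meaning to performance status, creatinine and bilirubin, so it does not carry a pregnancy exclusion. The investigator's judgement in 3.2 item 3 attaches to gastrointestinal and cardiac disorders only. The inpatient IL-2 guidelines cited in 4.0 and 4.1.1 concern dosing and management; they are not reproduced and are not presented as eligibility criteria.

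**Exposure in an affected patient.** Inputs are 21 temozolomide days and 2 IL-2 cycles per course (5.3), and approximately 12 weeks per course (6.1, Appendix III).

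- One course: 21 temozolomide days and 2 IL-2 cycles.
- Two courses: 2 x 21 = 42 temozolomide days and 2 x 2 = 4 IL-2 cycles.
- Four courses: 4 x 21 = 84 temozolomide days and 4 x 2 = 8 IL-2 cycles, over about 4 x 12 = 48 weeks.

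Four courses are a ceiling. Progression after course 1 ends treatment, and stable disease or complete response after course 1 allows one more course. Only patients with continuing partial or minor response, or a complete response reached late, could get that far.

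**What a single baseline test would cover.** Baseline may precede treatment by up to 28 days (Appendix III footnote 1). Cycle 2 follows about 10 days after discharge from Cycle 1, and temozolomide starts 28 days after discharge from Cycle 2. A baseline result could thus be 28 + 10 + 28 = 66 days old, plus two inpatient stays, at the first temozolomide dose. Routine labs are already scheduled at baseline, before each IL-2 cycle, on temozolomide Day 1 and after the course, so any repeat would need no new visit.

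**The case against.** The best counter-argument is that silence is not permission. Patients are invited by clinicians at one experienced centre, meeting the criteria does not oblige anyone to enrol a patient, and the consent pages and schema figure, which are not in the public text, may deal with pregnancy. Much of this stands. A reader might infer that the protocol positively allows pregnant patients in; it does not say so, and the accurate statement is that the written criteria do not exclude them. The consent form may well contain a warning. It would still not add a line to the eligibility lists or a test to the schedule, both of which are available in full.

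A reader might also take the birth-defect item in 7.0 as evidence that the plan foresees fetal harm from these drugs and yet ignores it at entry. The documents do not support that. The item is one of the general seriousness criteria and predicts nothing about IL-2 or temozolomide, so there is no internal contradiction.

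Nor can one say that a pregnancy would certainly be missed. History and physical examination are scheduled at baseline, before each IL-2 cycle and after each course, and body imaging at baseline and after each course. These might reveal a pregnancy, but they are no substitute for a test, so the fair wording is that it might not be detected.

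Finally, the 84 days over about 48 weeks should not be read as the expected exposure. It applies only to patients who go on to four courses, and assumes that a pregnancy passes unnoticed through repeated examinations.

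**Conclusion.** The concern holds as an omission from the visible eligibility criteria, checklist and schedule. A pregnant or breast-feeding patient would satisfy every written criterion that bears on the matter, and no scheduled laboratory test would look for a pregnancy. The conclusion rests on one outside assumption, that exposure to these drugs could harm a fetus or nursing infant. This is an inference from the drug class and the described toxicities; the documents neither state nor quantify it.

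The number affected is probably small out of at most 40. It cannot be estimated, because the documents give no age or sex mix. There is no effect on the response-rate analysis, the stage 1 rule of 12 patients or the total of 37. The point deserves action because the potential harm is serious and the correction is cheap.

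**What to change.** - Add pregnancy and breast-feeding to the exclusions in 3.2, with a matching line on the eligibility checklist.
- Add a pregnancy test for women of childbearing potential to 5.2 and to the baseline column of Appendix III, run on the routine blood sample already taken.
- Have the sponsor decide, and state, whether the test is repeated at the existing routine-lab points. The temozolomide Day 1 column should be considered explicitly alongside the pre-IL-2 columns, because of the interval shown above.
- Reconcile the eligibility, schedule, consent and safety text so that they agree. Contraception terms and the handling of a pregnancy found during treatment are for the sponsor to set.

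The cost is one exclusion line, one checklist line, one schedule row and an inexpensive assay on blood already drawn, with negligible loss of accrual. No change to the sample size or analysis is needed.

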4.0 TREATMENTS

The study drugs will be IL-2 aldesleukin (Proleukin), and temozolomide (Temodar). IL-2 will be given IV according to standard procedures using the Pittsburgh clinical guidelines for management. This is the current standard operating procedure on the PSCI inpatient clinical unit. The physicians, nursing and ancillary staff of this unit are very experienced in the delivery of high dose IL-2 and the management of the expected transient toxicities. There are several dosing regimens for temozolomide. Temozolomide is an oral chemotherapy agent and is dosed according to BSA. We will choose the chronic low dose regimen of temozolomide at 75 mg/m² daily as noted previously (8). This regimen is widely used for management of metastatic melanoma and is a standard regimen in the PSHCI melanoma clinic. It is extremely well tolerated.

4.1 High Dose IL-2: Dosage, Administration, Toxicity and its Management

Aldesleukin is currently an FDA approved drug for the treatment of metastatic melanoma and metastatic renal cell carcinoma. Only high dose regimens can reproducibly result in highly durable, complete responses and this is the current standard regimen at PSHCI

4.1.1 Aldesleukin Dosage, Administration and Dose Modifications

The dose of IL-2 is 600,000 International Units/kg given intravenously every 8 hours as tolerated by the Pittsburgh clinical guidelines for management up to a maximum of 14 doses. Patients rarely get to 14 doses. Patients are supported symptomatically and with fluid boluses. Vasopressors are not used. No dose modifications are utilized. Doses are held per the clinical guidelines.

4.1.2 Aldesleukin Drug Information

Aldesleukin is a recombinant produced natural human cytokine. It is manufactured by Novartis. It is given in very large doses. The mechanism of action is unclear but it results in expansion of T-cell populations and results in production of other cytokines including tumor necrosis factor. The administration is associated with characteristic severe but reversible toxicities for which care in a specialized unit is ideal and as is the case at PSHCI. Administration of HD IL-2 mimics acute bacterial sepsis with inflammatory constitutional symptoms and signs including rigors, high fever, lassitude, anorexia, somnolence, hypotension and capillary leak. The toxicities are

transient and resolve usually completely within 24 hours of stopping the drug. They are managed supportively with fluids, antiemetics, antipyretics and analgesics. Mortality due to high dose IL-2 in the current era is < 2%. We have not had a fatality due to this treatment at PSHCI. Dosing and withholding dosing is carefully regulated by a treatment algorithm developed at the UPMC.

4.1.3 Aldesleukin Potential Toxicities and their Management

> 10% rigors, fevers, diaphoresis, lassitude, somnolence, nausea, vomiting, anorexia, edema, water weight gain

1 to 10% transient bone marrow suppression, cholestasis, prerenal azotemia

< 1% delirium

4.2 Temozolomide: Dosage, Administration, Toxicity and its Management

Temozolomide is currently an FDA approved drug for the treatment of metastatic melanoma and primary brain tumors. It has also been used off label for brain metastases and low grade neuroendocrine tumors. It is manufactured by Schering-Plough.

4.2.1 Temozolomide Dosage, Administration and Dose Modifications

The dose of temozolomide is based on the BSA for the patient. Patients would receive temozolomide at 75 mg/m² at bedtime daily for 21 days beginning 28 days after discharge from Cycle 2 of high dose IL-2. Ondansetron 8mg po will be administered 30 minutes prior to and every morning after each dose of temozolomide. The medication is oral and is available in various doses to accommodate wide range of BSA. Typically, this low dose of temozolomide does not result in cytopenias requiring dose reduction. If, however, PLT are < 100 K or ANC is < 500, then the Temozolomide would be given with a 25% dose reduction for remaining cycles.

4.2.2 Temozolomide Drug Information

Temozolomide is a synthetic atypical alkylator. It can cross the blood brain barrier and has excellent bioavailability. Patients would be given Zofran and Compazine as antiemetic support.

4.2.3 Temozolomide Potential Toxicities and their Management

> 10% nausea, vomiting

1 to 10% fatigue

< 1% bone marrow suppression particularly platelets, immunosuppression, PCP pneumonia, secondary leukemia

5.0 TRIAL PROCEDURES

5.1 Screening and Consent

Patients with metastatic melanoma seen in the PSHCI clinic who are considered good candidates for high dose IL-2 therapy will be asked to participate in this trial and their eligibility will be reviewed using the inclusion and exclusion criteria noted. After explanation of the nature and logistical aspects of the study, patients will be asked to review the consent document carefully. If they have any questions regarding any aspect of the study, these will be answered to the satisfaction of the patient. The patient will sign the consent document to verify that they are fully interested in participation in the study as defined by the consent form. An eligibility checklist will be completed and signed by study personnel after consent has been executed (Appendix I Eligibility Checklist). The demographics and clinical plan data will be recorded on forms (Baseline Interval Form) (Recist 1.1 Measurement Form)

5.2 Baseline Evaluation

Patients will have an initial history and physical examination by the investigator. Patients will have baseline labs: CBC with differential, CMP, LDH, autoimmune panel and correlative science labs drawn, and will also have a baseline imaging with CT/PET or CT (CAP). A brain MRI will be obtained to evaluate for brain metastases. Patients will have a 2D and M-mode echocardiogram performed to assess ejection fraction and will have pulmonary function testing with carbon monoxide diffusion capacity testing (DLCO) to test for adequate cardiopulmonary reserve. These studies should be within 4 weeks of starting study treatment. See Appendix III Active Treatment Flow Chart/Time and Events Schedule which lists testing over time.

5.3 Therapy

After baseline studies have been completed, the patients would be admitted to the PSHCI inpatient clinical unit for Course 1 Cycle 1 of HD IL-2 treatment. Treatment will proceed according to the standard treatment algorithm utilized by the PSHCI inpatient clinical unit. Patients will be given as many doses of IL-2 up to a maximum of 14 at 8 hr intervals as allowed by the algorithm at 600,000 International Units/kg. Patients will receive standard supportive measures including fluid boluses, antiemetics and antipyretics as indicated. The patients will be discharged when the acute toxicities of the IL-2 have subsided. They will be reassessed on or about Day 10 after discharge from Cycle 1 and will be re-admitted for Cycle 2. After Cycle 2 of HD IL-2, they would begin temozolomide at 75 mg/m² on the 28th day after discharge and they would take it daily at bedtime for 21 days. Approximately 14 days after the final dose of temozolomide, patients will be assessed for response via imaging. The response determined after restaging post course 1 would determine the next step. Patients with progressive disease would go off study. Patients with a CR would receive one additional course of treatment and would then be observed. Patients with SD would receive one additional course of treatment. Patients with a PR or minor response would continue treatment up to a maximum of 4 courses (8 cycles HD IL-2 and 4 cycles of temozolomide). If they develop progressive disease at any time during this treatment then they would go off study. If they develop a CR then they would have one additional course of treatment provided this course does not make more than 4 total courses. If they have PR or minor response after course 2 then they would receive up to 2 additional courses.

5.5 Removal of Patients from Therapy

Patients can remove themselves from the study at any time for any reason. Patients will be removed from the study by an investigator for undue toxicity as determined by an investigator. Patients will also be removed if they demonstrate disease progression or stable disease as defined above.

5.6 Post-Study Follow-Up

After patients are off the study either for the reasons noted above or for completion of study therapy, then they will be followed for time to progression, progression free and overall survival by review of patient records. Follow up will be according to clinical practice this is generally every 6 months or less.

6.0 ASSESSMENTS

6.1 Clinical Assessments

The logistics of the study are summarized in the table, 15.1.8. Patients will be evaluated in the clinic by an investigator before each treatment cycle. Before each cycle of therapy, patients will have routine and correlative science labs performed along with a history and physical examination. These data will be recorded on a form (15.1.4 Clinical Evaluation). An adverse event form will also be completed at each of these evaluations by the study nurse-coordinator (see below). Patients will have staging performed with CT/PET or CT (CAP) after every complete course of treatment (2 complete cycles of HD IL-2 plus 4 weeks of rest plus 3 weeks of oral temozolomide plus 2 weeks of rest prior to reimaging = 1 complete course = approximately 12 weeks). Patients with measurable skin and/or subcutaneous lesions would have 2-dimensional measurements performed using a ruler after each complete course of therapy. They will also have an autoimmune panel drawn after each complete cycle. The autoimmune panel will include an ESR, CRP, ANA, RF, and TSH. Patients with known brain metastases will have repeat MRI of the head after each course. Patients with or without known brain metastases can get repeat MRI at any time should they develop neurologic symptoms as determined by the investigator. Response will be by modified RECIST criteria 1.1 and will employ the following definitions of response:

CR – complete response - no evidence of disease, 100% reduction in the volume of disease

PR – partial response - $\geq 50\%$ but $< 100\%$ reduction in volume of disease

MR – minor response - $\geq 25\%$ but $< 50\%$ reduction in volume of disease

SD – stable disease - $< 25\%$ increase in volume of disease to $< 25\%$ reduction in volume of disease

PD – progressive disease - $\geq 25\%$ increase in volume of disease

The final response will be the best response observed during the course of treatment while on study

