progression for at least eight weeks at the time of enrollment. Patients must not require corticosteroids for treatment of cerebral edema for brain metastases. Patients must be evaluated with a head MRI within 4 weeks prior to enrollment. Patients may have had prior dacarbazine or temozolomide since the mechanism of action of the temozolomide to be used in the context of this study is related more to effects on immune cells than to its known anti-melanoma effects. Patients would receive baseline staging imaging and laboratory assessment including study-specific immunologic correlative science testing. Patients would receive HD IL-2 according to standard procedure as in-patients on the PSHCI inpatient clinical unit. Patients would receive Cycle 1 of aldesleukin at 600,000 International Units/kg every 8 hours as tolerated up to a maximum of 14 doses. On or about day 10 after discharge from Cycle 1, they would be re-admitted for Cycle 2 of treatment. Then, 28 days after discharge from Cycle 2, they would receive temozolomide at 75 mg/m² daily for 21 days. Two cycles of HD IL-2 therapy as performed above plus 21 days of temozolomide would constitute one course of therapy. After this they would be scanned to assess response with CT/PET or CT(CAP). Responding patients (CR, PR, SD, Minor Response) would be given a 2nd course of treatment as above. Patients with a CR would receive one additional course of treatment and would then be observed. Patients with SD after 2nd course of treatment would go off study. Patients with a PR or Minor Response would continue treatment up to a maximum of 4 courses (8 cycles). If they develop Progressive Disease at any time during this treatment then they would go off study. If they develop a CR then they would have one additional course of treatment provided this course does not make more than 4 total courses. If they have PR or Minor Response after Course 2 then they would receive up to 2 additional courses.

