or MR) then accrual of an additional 25 patients will ensue. Three additional patients would be allowed to accrue to cover any early drop-outs (receipt of less than 2 complete cycles of treatment). Eligible patients would have baseline imaging with CT or CT/PET. A head MRI to rule out asymptomatic occult brain metastases will be performed on all patients as well. Patients with known brain metastases will have baseline MRI done as well and would then have follow-up MRIs performed after each course. An echocardiogram to check cardiac function and PFTs with DLCO will be performed in all patients to assure that they have adequate cardiopulmonary reserve to sustain HD IL-2 as is standard. Patients would have baseline laboratory testing done pre-treatment and at every cycle initiation. An autoimmune panel will be performed pre-treatment and after every cycle of treatment. Correlative science immunoassays will be performed pre-treatment and after every cycle of treatment. Response as per radiologic imaging assessment and physical assessment of accessible and measurable skin metastases if applicable will be performed after every course of treatment (2 cycles HD IL-2 and 21 days of temozolomide.). Response will be determined after course 1 of treatment as a complete response (CR), partial response (PR), minor response (MR), stable disease (SD) or progressive disease (PD) according to standard definitions of response. Patients with CR will receive another complete course of treatment and will then go off study except for follow-up. Patients with progressive disease (PD) will go off study after course 1. Patients with stable disease (SD) after course one will repeat one additional course maximum. Patients with PR or MR will continue with additional courses as determined by response up to a maximum of 4 courses total (8 cycles). Responses and their durability will be compared to known rates of response and their durability using HD IL-2 alone. For a population of 40, using standard HD IL-2, the expected response rate 10% would be in 4 of the 40 and the CR rate 5% in about 2 of the 40. We would hypothesize that we can at least double these at a minimum using the methods described in this protocol.

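### Response is labelled modified RECIST 1.1 but cut on percent change in tumour volume with no volume or summing rule, so the same lesion can change category at every boundary that drives a decision

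*Combined protocol and SAP*

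**What the plan says.** Section 6.1 sets the standard: "Response will be by modified RECIST criteria 1.1 and will employ the following definitions of response". CR is "no evidence of disease, 100% reduction in the volume of disease". PR is a volume reduction of at least 50% but short of 100%, MR a reduction of at least 25% but under 50%, and PD an increase of at least 25%. SD is what lies between MR and PD.

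The other pointers to measurement do not match a volume scale:
- Section 6.1, skin disease: "Patients with measurable skin and/or subcutaneous lesions would have 2-dimensional measurements performed using a ruler after each complete course of therapy".
- Section 5.1 names a "Recist 1.1 Measurement Form", whose content is not reproduced.
- Section 3.0 has the categories, ending in "stable disease (SD) or progressive disease (PD) according to standard definitions of response", without saying which standard.
- Section 6.1 has CT/PET or CT after each course, with no dimension, target-lesion, volume or summing rule.

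The categories are used as follows:
- Section 8.2 counts only CR and PR in the response rate and records TTP as the measure of durability.
- Section 8.1 calls the regimen effective with at least 4 responses.
- Section 3.0 opens stage 2 on a CR, a PR "or MR) then accrual of an additional 25 patients will ensue".
- Sections 3.0, 5.3 and 5.5 take PD off study.
- Section 3.0: "Patients with stable disease (SD) after course one will repeat one additional course maximum". Section 1.3: "Patients with SD after 2nd course of treatment would go off study". Under section 5.3, PR or MR after course 2 may bring up to two more courses.

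**The concern.** The label, the form and the ruler measurement point to diameters or to two dimensions, while the cut-offs are on volume. Two assessors who both follow the protocol could put the same lesion in different categories.

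Each boundary carries a decision:
- **PR or MR** decides whether a patient counts towards the 4 responses needed. Continuation is the same for both.
- **MR or SD** can decide whether stage 2 opens and, after course 2, whether treatment goes on.
- **SD or PD** decides removal from study and the date of progression in TTP.

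The literal volume reading also makes PD easy to reach: a small increase in diameter ends treatment.

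**Working it through.** **1. The plan's own design figure.** Inputs from section 8.1: n1 = 12, stop at 0 responses; N = 37, success at 4 or more; p0 = 0.05, p1 = 0.20. With X ~ Bin(12, p) and Y ~ Bin(25, p),

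P(success) = Σ over x = 1 to 12 of P(X = x) · P(Y ≥ max(0, 4 − x)).

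This gives 0.0935 at p = 0.05 and 0.9024 at p = 0.20, within the stated α = β = 0.10. The chance of stopping at stage 1 under p0 is 0.95^12 = 0.540. The design reproduces; the issue is what counts as a response.

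**2. Diameter change at each cut-off.** Assume one lesion changing uniformly, with diameter ratio k. A volume scales as k³, a product of two diameters as k², one diameter as k. For a cut-off ratio c (0.50 for PR, 0.75 for MR, 1.25 for PD), k = c^(1/3), c^(1/2) or c.

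| Cut-off | Volume | Two-diameter product | One diameter |
|---|---|---|---|
| PR (c = 0.50) | 0.794: −20.6% | 0.707: −29.3% | 0.50: −50% |
| MR (c = 0.75) | 0.909: −9.1% | 0.866: −13.4% | 0.75: −25% |
| PD (c = 1.25) | 1.077: +7.7% | 1.118: +11.8% | 1.25: +25% |

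**3. The cut-offs in millimetres from a 20 mm baseline** (20 × k):
- PR/MR: 15.9, 14.1 or 10.0 mm.
- MR/SD: 18.2, 17.3 or 15.0 mm.
- SD/PD: 21.5, 22.4 or 25.0 mm.

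The three readings together therefore leave the category open between 10.0 and 15.9 mm for PR/MR, 15.0 and 18.2 mm for MR/SD, and 21.5 and 25.0 mm for SD/PD.

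**4. Worked lesions from 20 mm.**

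| Now | Volume | Product | Diameter |
|---|---|---|---|
| 15 mm (k = 0.75) | 0.75³ = 0.422: −57.8%, PR | 0.75² = 0.5625: −43.8%, MR | −25%, MR |
| 15.6 mm (k = 0.78) | −52.5%, PR | −39.2%, MR | −22%, SD |
| 18 mm (k = 0.90) | 0.9³ = 0.729: −27.1%, MR | 0.9² = 0.81: −19.0%, SD | −10%, SD |
| 22 mm (k = 1.10) | 1.1³ = 1.331: +33.1%, PD | 1.1² = 1.21: +21.0%, SD | +10%, SD |

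The 15.6 mm lesion falls in three different categories.

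**5. Illustrations only; the inputs here are assumptions with no source in the documents.**
- *False-positive rate.* If a looser PR cut-off raised the response rate of an ineffective regimen from 5% to 6% or 7.5%, the formula in step 1 would give 15.1% or 25.6% instead of 9.3%.
- *False PD in one unchanged lesion.* Assume independent normal error on each measured diameter, with coefficient of variation s. If one diameter is cubed, P = 1 − Φ((k − 1)/(s·√(1 + k²))) with k = 1.0772. At s = 5% this is 1 − Φ(0.0772/0.0735) = 14.7%. By simulation under the same error model, three measured axes give 3.5% and a two-diameter product 1.3%.
- *False PD with three equal lesions summed, s = 5%.* The same three figures fall to 3.4%, 0.08% and 0.005% (simulated).

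**The case against.** The strongest reply is that the text says volume, so volume is meant. Under uniform change every consistent volume method gives the same percent change: 20 to 15 mm is −57.8% whether sphere, ellipsoid or segmentation is used. The product is an area, the plan never mentions one, and two-dimensional measurement is prescribed only for skin and subcutaneous lesions. This stands in part. The product and diameter readings of CT lesions are possible readings prompted by the RECIST label and form, not rival ways of computing a volume. It does not rescue the plan, because two ruler dimensions give no volume without a further rule, no CT or summing rule is stated, and the literal reading is the one under which 7.7% growth is PD.

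A second reply is that an extra MR at stage 1 does little to the error rate. That is right: if the gate never stopped the trial, the false-positive rate at p0 would be P(X ≥ 4 of 37) = 11.2% rather than 9.3%. The cost is 25 more patients treated, not a large loss of error control. Counting MR at the gate but not in the final numerator is a separate inconsistency.

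A reader might go further and infer any of the following, none of which the documents support:
- **The response rate is biased upwards, with a false-positive rate of 15% to 26%.** The documents give no distribution of tumour change, so the shifted null rates are invented inputs.
- **p0 = 5% is wrong.** It is the low end of the historical 5–10% in section 1.3. The criteria behind that range are not stated, so a mismatch is neither shown nor excluded.
- **Many patients will be removed for false progression.** That depends on the assumed measurement error, the number of lesions and whether one diameter is cubed. With three lesions at 5% error it is negligible unless one is.

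**Conclusion.** The concern holds as a defect in how the primary endpoint is defined. The stated standard, the named form and the only stated dimension of measurement do not agree with the scale of the cut-offs. Depending on the reading, PR needs 20.6% to 50% shrinkage in diameter and PD 7.7% to 25% growth. With success set at 4 of 37, reclassifying a single patient can change the conclusion.

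The diameter equivalents assume one lesion changing uniformly; irregular change and sums over several lesions will differ. The size and direction of any bias in CR+PR are unknown. The sample size is sound and does not change. Confidence is high for the definitional gap and does not extend to the illustrations in step 5.

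**What to change.** Score the primary CR+PR endpoint, off-study PD and TTP by RECIST 1.1 on the sum of diameters, using the form named in section 5.1. Keep the volume categories as secondary. Where MR is used for continuation or the stage 1 gate, give it a diameter range. Its present 25% cut-off corresponds to 9.1%, 13.4% or 25% shrinkage, so the sponsor should say which was meant. The ruler measurements of skin lesions already contain a diameter.

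If volume is to stay primary, state one derivation and one summing rule for CT and skin lesions, and set cut-offs matched to diameter. The RECIST cut-offs are not printed in the documents. Assuming −30% and +20%, the matched volume cut-offs are 0.7³ − 1 = −65.7% and 1.2³ − 1 = +72.8%. Over −25% to −35% and +15% to +25% they run from −57.8% to −72.5% and from +52.1% to +95.3%.

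The cost is wording in sections 6.1 and 8.2 and in the continuation text of 1.3, 3.0 and 5.3, with no extra scans and no change in sample size. The form should be checked to confirm that it records diameters, since it is not reproduced.

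The downside is that fewer patients qualify as PR than under literal volume, and some with modest growth stay on as SD for one more course. This holds for any PR cut-off beyond 20.6% shrinkage and any PD cut-off above 7.7% growth. At an assumed −30%, PR changes little from the product reading (29.3%) and is easier to reach than under the one-diameter reading of section 6.1 (50%).
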